9.1.2. Secondary Objectives

1. Describe and quantify the toxicity profile of the combination of 5AC + GM-CSF
2. Determine the impact on one year RFS and overall survival for poor risk myeloid disorders following maintenance therapy with 5AC + GM-CSF
3. Describe the changes in the clonogenic population, including changes in detectable cytogenetic abnormalities in blood and marrow, during maintenance therapy.

9.2. Study Design

This will be a three-arm phase II study with historical references for each arm. The historical two-year RFS and corresponding event rates in these arms are assumed to be: myeloablative, 40% (0.46 per person year); non-myeloablative, 34% (0.54 per person year); and standard consolidation, 20% (0.80 per person year). The non-parametric Kaplan-Meier estimate will be used to monitor the relapse-free survival function in each cohort.

9.3. Futility Analysis

After 10 patients have been enrolled in an arm, the design will include interim analyses for futility that could halt that arm of the trial if it seems likely that the combination of 5AC and GM-CSF does not have sufficient clinical activity. The study is designed to stop any arm if it is 70% certain that the two-year RFS is below the historical two-year RFS: 40% in the myeloablative arm, 34% in the non-myeloablative arm, and 20% in the standard consolidation group.

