9.4. Early Stopping Guideline for Futility and Simulations for Each Cohort

The simulation studies demonstrate the power for a sample size of 25 in each cohort. The study will be monitored for futility with a primary endpoint of two-year RFS. If the study meets the accrual goal of 10 patients per year per arm, 20 patients would be accrued by the time the first patient enrolled on study reaches the two-year efficacy endpoint. We will therefore monitor the study based on one-year RFS, knowing that if the one-year RFS is convincingly less than our targeted RFS at two years, the study would not meet its efficacy

objective and the trial should be halted. The non-parametric Kaplan-Meier estimate will be used to estimate the RFS function at one year.

The sample size of 25 and the study design operating characteristics assume a 2.5 year accrual period with an additional follow-up of one year. The null two-year RFS is 40% in the myeloablative group, 34% in the non-myeloablative group and 20% in the non-transplant cohort. We have designed each arm to stop early only if the posterior probability is 70% or higher that one-year RFS is less than that arm's null two-year RFS. Simulations were carried out with exponential survival and staggered patient entry. We assumed on average 10 patients will enter each arm of the study per year. Initial interim analyses occurred after 10 patients enrolled and was repeated every 5th patient to the maximum of 25. The interim analysis estimates of one-year RFS are based on analyses with an underlying Dirichlet process prior. We approximate the posterior distribution, which is actually a mixture of Beta distributions, the mixture depending on the amount of censoring, with a single Beta distribution. The parameters of this posterior Beta distribution are based on the number of failures and the effective sample size at one year, combined with the parameters of the prior.

The following tables summarize the operating characteristics under various scenarios for the underlying exponential RFS, based on 1000 simulations. The uncertainty of the null two-year RFS estimates are characterized with three priors: beta(2,3) in the myeloablative group (Table 5) and beta(2,4) in the non-myeloablative group (Table 6) and beta(1,4) in the non-transplant group (Table 7). This implies that our prior guess at the two year RFS for these three cohorts are respectively 40, 34 and 20%.

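### Sections 9.3 and 9.4 give two incompatible futility rules, and the one likely to be run compares one-year RFS with a two-year threshold

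*Combined protocol and SAP*

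**What the plan says.** Section 9.3 defines futility on the primary time point: "The study is designed to stop any arm if it is 70% certain that the two-year RFS is below the historical two-year RFS", with benchmarks of 40%, 34% and 20%. It mentions no one-year surrogate and does not refer forward to 9.4.

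Section 9.4 observes that, at the planned accrual, 20 patients per arm would be enrolled before the first reaches two years. It concludes: "We will therefore monitor the study based on one-year RFS". The reason offered is that the study could not meet its objective "if the one-year RFS is convincingly less than our targeted RFS at two years". The rule itself is then that an arm may "stop early only if the posterior probability is 70% or higher that one-year RFS is less than that arm's null two-year RFS". The benchmark is restated: "The null two-year RFS is 40% in the myeloablative group, 34% in the non-myeloablative group and 20% in the non-transplant cohort".

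Section 9.2 gives the historical two-year RFS with event rates: "myeloablative, 40% (0.46 per person year); non-myeloablative, 34% (0.54 per person year); and standard consolidation, 20% (0.80 per person year". The priors in 9.4 are "beta(2,3) in the myeloablative group (Table 5) and beta(2,4) in the non-myeloablative group (Table 6) and beta(1,4) in the non-transplant group (Table 7". Looks start at 10 patients and repeat every fifth patient up to 25. The text before Table 5 says the risk of not stopping an arm that performs at the historical RFS rates is about one half in all three arms, and accepts the rule on that basis.

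**The concern.** One section says an arm stops if a condition on two-year RFS is met. The next says it stops only if a different condition, on one-year RFS, is met. The 70% cut-off and the benchmarks are identical, so the difference lies wholly in the quantity compared with them. Both instructions cannot be followed when the two-year condition holds and the one-year condition does not.

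Two things are at stake. First, anyone applying 9.3 and anyone applying 9.4 can reach opposite decisions on the same patients. Second, if 9.4 is what will be run, a one-year proportion is held against a two-year benchmark. An arm no better than history would then almost never close, although the plan tells its reviewers that such an arm closes about half the time.

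**Working it through.** **Inputs.** Benchmarks 0.40/0.34/0.20 (9.3, 9.4); event rates h = 0.46/0.54/0.80 per person-year (9.2); priors beta(2,3), beta(2,4), beta(1,4); cut-off 0.70; exponential RFS (9.4); target medians 3.1 years, 3.1 years and 18 months (text before Table 5). Arms are in the order myeloablative / non-myeloablative / consolidation throughout.

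**Method.** With s of n patients relapse-free at the relevant time point, the posterior is Beta(a+s, b+n−s). Stop if its CDF at the benchmark is at least 0.70. Looks are at n = 10, 15 and 20, and stopping probabilities come from exact binomial recursion. Outcomes are taken as complete at each look. That is an idealisation: two-year data would mostly be unavailable at these looks.

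**Step 1: reproduce the plan.** Apply the 9.4 rule with true one-year RFS set equal to the benchmark, as in the null rows of Tables 5-7.

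| Arm | Plan, P(stop) | Exact |
|---|---|---|
| Myeloablative (0.40) | 0.46 | 0.440 |
| Non-myeloablative (0.34) | 0.45 | 0.450 |
| Consolidation (0.20) | 0.52 | 0.537 |

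All three agree within 2 points. Monte Carlo error for 1000 simulations is up to about 1.96 × √(0.25/1000) = 3 points. The tables therefore describe the 9.4 rule, at a one-year RFS equal to the historical two-year figure.

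**Step 2: what the historical rates mean at one year.** One-year RFS = exp(−h): exp(−0.46) = 0.63, exp(−0.54) = 0.58, exp(−0.80) = 0.45. Two-year RFS = exp(−2h) = 0.40, 0.34, 0.20. A historical-rate arm is therefore not in the null rows of the tables. It sits at a one-year RFS of 0.63/0.58/0.45.

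**Step 3: probability of stopping an arm at the historical rates.**

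| Rule | Myeloablative | Non-myeloablative | Consolidation |
|---|---|---|---|
| 9.3: two-year RFS against the two-year benchmark | 44% | 45% | 53% |
| 9.3 put on the one-year scale by the exponential model, same priors | 65% | 75% | 62% |
| 9.4: one-year RFS against the two-year benchmark | 4% | 2% | 3% |

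Simulating staggered entry with different definitions of effective sample size moves the 9.4 row to between 2% and 14%. The risk of not stopping is then 86% to 98%, not about one half.

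**Step 4: the same patients under both rules, with no survival model.** Ten patients per arm, all followed for two years:

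| Arm | Relapse-free at 1 y, 2 y | 9.4 posterior probability | 9.3 posterior probability |
|---|---|---|---|
| Myeloablative | 5, 2 | Beta(7,8) below 0.40: 0.31, continue | Beta(4,11) below 0.40: 0.88, stop |
| Non-myeloablative | 5, 2 | Beta(7,9) below 0.34: 0.22, continue | Beta(4,12) below 0.34: 0.81, stop |
| Consolidation | 3, 1 | Beta(4,11) below 0.20: 0.30, continue | Beta(2,13) below 0.20: 0.80, stop |

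The conflict runs one way. The number relapse-free at one year is never smaller than the number at two years, so data that stop an arm under 9.4 also stop it under 9.3, but not the reverse.

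**The case against.** The best defence is that the operative rule can be identified. Section 9.4 explains why two-year data come too late, announces the switch to one-year RFS, and alone supplies looks, priors, a posterior method and operating characteristics. Section 9.3 can be read as a general statement that 9.4 implements. A two-year rule could hardly act at 10 to 20 patients anyway, and the 9.3 stopping probability depends on how it is computed (44/45/53% or 65/75/62%). On this view, aligning the wording of 9.3 is enough.

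Much of this stands: 9.4 is the likely rule, and the 9.3 figures are idealised. But 9.3 is not worded as superseded, and the reason given for using one-year data does not explain keeping a two-year threshold. Rewording 9.3 alone would remove the contradiction and leave a rule that misses a historical-rate arm at least 86% of the time in every variant examined.

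A reader might also infer a third rule from the clause "if the one-year RFS is convincingly less than our targeted RFS at two years". Taking the target medians gives two-year RFS of 0.5^(2/3.1) = 0.64 in the transplant arms and 0.5^(2/1.5) = 0.40 in consolidation. With a 70% cut-off, an arm at target would then close 14/35/12% of the time. The documents do not support that reading. The clause is a rationale with no number and no probability cut-off. The 70% is borrowed, and at 80% the figures fall to 4/14/4%. Nor does the rationale contradict the 9.4 rule: if one-year RFS is below the two-year null, two-year RFS is below both null and target. The clause is loosely worded, no more.

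**Conclusion.** The point holds as a conflict between two rules, not three. Sections 9.3 and 9.4 cannot both be followed, and 9.4, the likely operative rule, does not do what 9.3 says the study is designed to do. At the historical rates the chance of closing an arm is 44/45/53% under 9.3 and about 4/2/3% under 9.4, so the claim that an ineffective arm goes unstopped about half the time is not true of the rule as written.

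The magnitudes rest on the plan's priors, looks at 10, 15 and 20, the exponential rates of 9.2 and complete outcomes. Staggered entry widens the 9.4 range to 2-14% without changing the conclusion. The opposite decisions in step 4 need no survival model, but they do need two-year follow-up on the ten patients.

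**What to change.** State one rule in both sections, with data and threshold at the same time point. One option keeps early monitoring: stop an arm if the posterior probability is at least 70% that one-year RFS is below that arm's historical one-year RFS implied by 9.2 (0.63/0.58/0.45). Centre the prior on that value and keep the present prior weight (a+b = 5, 6, 5). Reword the targeted-RFS clause to name the benchmark actually used. Regenerate Tables 5-7 with the historical one-year RFS as the null row, and correct the statement about the risk of not stopping.

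By the same recursion with complete outcomes, this rule stops about 42/37/39% of the time at the historical rates. At the target medians it stops 4/1/4%.

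The cost is wording in two sections and rerun simulations. The downside is that an arm at target is stopped about 1-4% of the time instead of under 1%. In the non-myeloablative and consolidation arms the rule also stops somewhat less often at the historical rates than the 45% and 53% computed for 9.3. If the sponsor prefers a different balance, the cut-off can be tuned once the null is correctly placed.

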9.4. Early Stopping Guideline for Futility and Simulations for Each Cohort

The simulation studies demonstrate the power for a sample size of 25 in each cohort. The study will be monitored for futility with a primary endpoint of two-year RFS. If the study meets the accrual goal of 10 patients per year per arm, 20 patients would be accrued by the time the first patient enrolled on study reaches the two-year efficacy endpoint. We will therefore monitor the study based on one-year RFS, knowing that if the one-year RFS is convincingly less than our targeted RFS at two years, the study would not meet its efficacy

objective and the trial should be halted. The non-parametric Kaplan-Meier estimate will be used to estimate the RFS function at one year.

The sample size of 25 and the study design operating characteristics assume a 2.5 year accrual period with an additional follow-up of one year. The null two-year RFS is 40% in the myeloablative group, 34% in the non-myeloablative group and 20% in the non-transplant cohort. We have designed each arm to stop early only if the posterior probability is 70% or higher that one-year RFS is less than that arm's null two-year RFS. Simulations were carried out with exponential survival and staggered patient entry. We assumed on average 10 patients will enter each arm of the study per year. Initial interim analyses occurred after 10 patients enrolled and was repeated every 5th patient to the maximum of 25. The interim analysis estimates of one-year RFS are based on analyses with an underlying Dirichlet process prior. We approximate the posterior distribution, which is actually a mixture of Beta distributions, the mixture depending on the amount of censoring, with a single Beta distribution. The parameters of this posterior Beta distribution are based on the number of failures and the effective sample size at one year, combined with the parameters of the prior.

The following tables summarize the operating characteristics under various scenarios for the underlying exponential RFS, based on 1000 simulations. The uncertainty of the null two-year RFS estimates are characterized with three priors: beta(2,3) in the myeloablative group (Table 5) and beta(2,4) in the non-myeloablative group (Table 6) and beta(1,4) in the non-transplant group (Table 7). This implies that our prior guess at the two year RFS for these three cohorts are respectively 40, 34 and 20%.

The highlighted row gives the power of the study under the scenario where the median RFS is increased from 1.5 to 3.1 years in myeloablative patients, 1.3 to 3.1 years in non-myeloablative patients and 10.4 months to 18 months in the non-transplant patients. The 95% posterior intervals are the quantiles of the simulated one-year RFS corresponding to probabilities of .025 and .957. The interpretation is that the posterior probability that the estimate of one-year RFS lies in this interval is 95%.

These futility stopping rules are not excessively stringent: for instance the risk of not stopping the arm if the treatment is equal to the null hypothesis (the historical RFS rates), and therefore not effective, is approximately 50% in all three arms. However, we do not want to accept the null hypothesis and stop the trial if there is a reasonable probability that the experimental treatment may be effective. The treatment is relatively non-toxic, we are monitoring toxicities and adjusting doses accordingly, the risk of relapse is very high, and upon relapse the mortality rate is very high. Therefore, we are willing to accept the characteristics of these stopping rules.

Table 5

1year RFS	Prob Stop for Futility	Avg N	Estimated 1 yr RFS	lo 95% Post Int'l	hi 95% Post Int'l	Prob H0 Rejected (power)
0.20	0.95	11.22	0.185	0.0	0.36	0.0
0.30	0.77	14.26	0.264	0.0	0.48	0.01
0.40	0.46	18.51	0.360	0.1	0.60	0.09
0.50	0.16	22.68	0.487	0.2	0.72	0.36
0.60	0.06	24.07	0.588	0.3	0.80	0.69

Myeloablative: prior is beta(2,3) : Mean is 0.40

Table 6

1year RFS	Prob Stop for Futility	Avg N	Estimated 1 yr RFS	lo 95% Post Int'l	hi 95% Post Int'l	Prob H0 Rejected (power)
0.20	0.86	13.22	0.178	0.0	0.36	0.01
0.34	0.45	19.2	0.307	0.1	0.52	0.13
0.40	0.30	21.16	0.364	0.1	0.56	0.24
0.50	0.09	23.86	0.485	0.2	0.68	0.58
0.60	0.02	24.73	0.59	0.36	0.80	0.88

Non-myeloablative: prior is beta(2,4) : Mean is 0.34

Table 7

1year RFS	Prob Stop for Futility	Avg N	Estimated 1 yr RFS	lo 95% Post Int'l	hi 95% Post Int'l	Prob H0 Rejected (power)
0.10	0.92	12.35	0.081	0.0	0.20	0.0
0.20	0.52	18.17	0.168	0.0	0.36	0.08
0.30	0.20	22.25	0.277	0.0	0.48	0.36
0.40	0.06	24.2	0.390	0.10	0.60	0.74
0.50	0.01	24.87	0.502	0.32	0.68	0.95

Non-transplant : prior is beta(1,4) : Mean is 0.20

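### The 3.1-year median RFS target for the two transplant arms matches no row of Tables 5 and 6, so the plan gives no power for the effect it names

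*Combined protocol and SAP*

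**What the plan says.** Section 9.4 presents the simulations as the support for the sample size: "The simulation studies demonstrate the power for a sample size of 25 in each cohort". The survival model is stated: "Simulations were carried out with exponential survival and staggered patient entry". The nulls are two-year figures: "The null two-year RFS is 40% in the myeloablative group, 34% in the non-myeloablative group and 20% in the non-transplant cohort". Section 9.2 gives the matching event rates of 0.46, 0.54 and 0.80 per person-year.

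The effect size is linked to the power in one sentence before Table 5. It begins "The highlighted row gives the power of the study under the scenario where the median RFS is increased". For the transplant arms it continues "median RFS is increased from 1.5 to 3.1 years in myeloablative patients, 1.3 to 3.1 years in non-myeloablative patients", and for consolidation "10.4 months to 18 months in the non-transplant patients".

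The first column of Tables 5 to 7 is headed 1year RFS. The highest row is 0.60 in Table 5 (power 0.69), 0.60 in Table 6 (power 0.88) and 0.50 in Table 7 (power 0.95). The 0.40 row of Table 7 has power 0.74.

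**The concern.** Under an exponential model a median fixes RFS at every time point, so each median in that sentence should lead to a row of its table. The 3.1-year target does not, at one year or at two. That sentence is the only place where the power of 25 patients per arm is tied to a clinical effect. If target and row do not belong together, a reader cannot tell what improvement 25 transplant patients can detect, or with what probability.

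**Working it through.** **Inputs.** Medians, exponential model, nulls, priors, futility rule and tables: section 9.4. Event rates: section 9.2.

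**Step 1: convert medians to RFS.** S(t) = 0.5^(t/median).

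| Median in section 9.4 | S(1 year) | S(2 years) | Matching table row |
|---|---|---|---|
| 1.5 y (myeloablative null) | 0.63 | 0.397 | 0.40, Table 5, two-year only |
| 1.3 y (non-myeloablative null) | 0.59 | 0.344 | 0.34, Table 6, two-year only |
| 10.4 mo (consolidation null) | 0.45 | 0.202 | 0.20, Table 7, two-year only |
| 18 mo (consolidation target) | 0.63 | 0.397 | 0.40, Table 7, two-year only |
| 3.1 y (both transplant targets) | 0.80 | 0.639 | none |

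If 3.1 is rounded from 3.05-3.15, two-year RFS is 0.635-0.644, so rounding of the median does not reach 0.60.

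**Step 2: what the 0.60 row means.**
- As two-year RFS: median = 2 × ln 2 / (−ln 0.60) = 1.386/0.511 = 2.71 years.
- As one-year RFS: median = ln 2 / (−ln 0.60) = 0.693/0.511 = 1.36 years. This is below the myeloablative null median of 1.5 years and barely above the non-myeloablative 1.3 years.

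**Step 3: hazard ratios.** The stated target is 1.5/3.1 = 0.48 (myeloablative) and 1.3/3.1 = 0.42 (non-myeloablative). From the rows on the two-year scale:
- myeloablative: ln 0.60/ln 0.40 = 0.56
- non-myeloablative: ln 0.60/ln 0.34 = 0.47
- consolidation: ln 0.40/ln 0.20 = 0.57

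**Step 4: reproduce the 0.60 rows.** I used an exact sequential binomial with n = 25, looks at 10, 15 and 20, a Beta posterior with the plan's prior, and stopping when Pr(RFS < null) ≥ 0.70. Every patient's status is taken as known, so censoring is ignored. Arms stop at:
- Table 5: ≤3/10, ≤4/15 or ≤6/20 patients relapse-free
- Table 6: ≤2/10, ≤4/15 or ≤5/20 patients relapse-free

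The plan gives no criterion for rejecting H0, so power is shown for the two final cuts that bracket the printed value.

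| At 0.60 | Stop | Average N | Power |
|---|---|---|---|
| Table 5, computed | 0.057 | 24.16 | 0.722 (≥14/25), 0.582 (≥15/25) |
| Table 5, printed | 0.06 | 24.07 | 0.69 |
| Table 6, computed | 0.017 | 24.77 | 0.917 (≥12/25), 0.844 (≥13/25) |
| Table 6, printed | 0.02 | 24.73 | 0.88 |

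The futility columns come out close to print. The power is bracketed, not reproduced.

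**Step 5: power at the stated target.**

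| RFS at a 3.1-year median | Myeloablative | Non-myeloablative |
|---|---|---|
| 0.639 (two-year scale) | 0.73 (≥15) to 0.84 (≥14) | 0.92 (≥13) to 0.96 (≥12) |
| 0.80 (one-year scale) | above 0.99 | above 0.99 |

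Interpolating between the two cuts so that the 0.60 row returns the printed power gives about 0.81 and 0.94 at 0.639. Against print that is about 12 points (0.81 − 0.69) and 6 points (0.94 − 0.88).

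**The case against.** **The highlighting cannot be seen.** Attaching 0.69 and 0.88 to the 3.1-year target assumes the shaded row is the 0.60 row. That stands as an assumption. It does not rescue the sentence, because no other row fits 3.1 years either.

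**The power figures depend on an assumed cut.** This also stands, and is why they are given as ranges. The mismatch itself needs only the conversion in step 1.

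**The effect is small and in the safe direction.** On the two-year scale the gap is 0.64 against 0.60, and the printed power is below the power for the named effect. This stands and limits the weight of the point.

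A reader might infer more than the documents support:

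- *Only the two transplant targets are wrong.* That holds only if the column is two-year RFS. On the printed label, 18 months is 0.63 and Table 7 stops at 0.50, so the consolidation target is off its table too.
- *The target should simply read 2.7 years.* That assumes both the 0.60 row and the two-year scale. The documents do not say whether the median or the table is at fault; 3.1 years gives 0.80 at one year, so an omitted row is equally possible.
- *69% and 88% are really close to false-positive rates.* On the one-year label, the historical medians already imply 0.63 and 0.59, so the 0.60 row would show essentially no improvement. But section 9.4 also says that the chance of not stopping at the historical rates is about 50%. That agrees with the stopping probabilities of 0.46, 0.45 and 0.52 in the 0.40, 0.34 and 0.20 rows, so the plan itself treats those rows as the two-year nulls. The scale is unresolved, and this reading cannot be asserted.

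**Conclusion.** The inconsistency is real. Under the plan's own exponential model, a 3.1-year median is 0.80 at one year or 0.64 at two, and neither is in Table 5 or 6. Whichever row was highlighted, its power is not the power for the stated transplant-arm effect.

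If the 0.60 row is meant and the scale is two-year RFS, the printed 0.69 compares with about 0.73-0.84, and the printed 0.88 with about 0.92-0.96. These ranges assume complete outcome data and the two cuts shown. The printed figures are then conservative, so this is no evidence that the transplant arms are underpowered for a 3.1-year median. Beneath it lies an unsettled time scale: the label says one year, while every median that fits a row does so at two years. This is a reporting error in a design figure that should be corrected; it does not affect the validity of the trial's conduct.

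**What to change.** In section 9.4, state in words which row, which time scale and which rule for rejecting H0 the quoted power refers to. If two-year RFS is meant, correct the column heading in Tables 5 to 7. Then make target and power agree in one of two ways:

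- (a) Keep the 0.60 row and restate the transplant-arm target as the median it implies, which is 2.7 years if the scale is two-year RFS.
- (b) Keep 3.1 years, add the matching row to Tables 5 and 6 (0.64 on the two-year scale, 0.80 on the one-year scale), and quote that row's power from the plan's own simulation.

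If hazard ratios are added, derive all three on one basis; from the rows on the two-year scale they are 0.56, 0.47 and 0.57.

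The cost is some rewording, or one more simulated row in each of two tables. Sample size and conduct are unchanged.

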9.1. Objectives

9.1.1. Primary Objective

The **primary objective** of the trial is to evaluate the two year relapse-free survival (RFS) of maintenance treatment with 5AC in combination with GM-CSF in patients with poor-risk Acute Myeloid Leukemia (AML) and Myelodysplasia (MDS) in

complete remission after definitive therapy with either a stem cell transplant or consolidation therapy with chemotherapy. RFS will be defined as time to relapse or death. The start time of RFS will be the date of first remission marrow following induction treatment. Patients will be required to have no morphologic evidence of leukemia or active MDS before entry onto the protocol. This study will monitor three separate cohorts:

1. Patients in complete remission (CR) following a full myeloablative stem cell transplant
2. Patients in CR following a non-myeloablative stem cell transplant
3. Patients in CR following standard consolidation therapy

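### The stated 50% risk of not stopping an ineffective arm reads two-year historical rates on a one-year axis; at the historical one-year rates the plan's own tables give 94% or more

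*Combined protocol and SAP*

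**What the plan says.** Section 9.2 sets the historical reference for each arm: "The historical two-year RFS and corresponding event rates in these arms are assumed to be: myeloablative, 40% (0.46 per person year"), then 34% (0.54 per person-year) for non-myeloablative transplant and 20% (0.80 per person-year) for standard consolidation. All three are two-year figures.

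The futility rule is worded in two ways. Section 9.3: "The study is designed to stop any arm if it is 70% certain that the two-year RFS is below the historical two-year RFS". Section 9.4 monitors one-year RFS instead, because accrual would be nearly complete before two-year data exist, and would "stop early only if the posterior probability is 70% or higher that one-year RFS is less than that arm's null two-year RFS". Section 9.4 simulates exponential survival with staggered entry at 10 patients per arm per year. Looks start at 10 patients and recur every fifth patient up to 25.

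The priors are beta(2,3), beta(2,4) and beta(1,4). The plan says of them: "This implies that our prior guess at the two year RFS for these three cohorts are respectively 40, 34 and 20"%. They are then updated with one-year data: "The parameters of this posterior Beta distribution are based on the number of failures and the effective sample size at one year".

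Tables 5 to 7 are indexed by one-year RFS and also report the estimated one-year RFS. From them the plan concludes that the risk of not stopping "if the treatment is equal to the null hypothesis (the historical RFS rates), and therefore not effective, is approximately 50% in all three arms". On power it says: "The highlighted row gives the power of the study under the scenario where the median RFS is increased from 1.5 to 3.1 years" in the myeloablative arm, from 1.3 to 3.1 years in the non-myeloablative arm and from 10.4 to 18 months in the non-transplant arm.

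**The concern.** A one-year RFS of 40% and a two-year RFS of 40% describe very different hazards. The 50% figure treats the rows at 0.40, 0.34 and 0.20 as the historical null, although the tables are on a one-year scale and the historical values are two-year values. An arm at the historical hazard has a much higher one-year RFS, where the tables show stopping to be rare.

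The sentence tells the IRB and the monitoring group how often an arm no better than history would run to full size, and it forms part of the argument for accepting the rule. If it is wrong, those readers believe that the screen removes about half of such arms when it removes very few. The same mix of scales affects the power statement, since the stated alternatives must also be placed on the one-year axis.

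**Working it through.** **1. Reproduce the stated figure.** One minus the tabled stopping probability at one-year RFS 0.40 (Table 5), 0.34 (Table 6) and 0.20 (Table 7):

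1 − 0.46 = 0.54; 1 − 0.45 = 0.55; 1 − 0.52 = 0.48.

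These are the rows behind the 50%.

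**2. Convert the historical rates.** With exponential survival, h = −ln S(2)/2 and S(1) = √S(2).

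| Arm | Two-year RFS (9.2) | h per year | One-year RFS | Median implied by h | Median if the same number is a one-year rate |
|---|---|---|---|---|---|
| Myeloablative | 0.40 | 0.458 | 0.632 | 18.2 months | 9.1 months |
| Non-myeloablative | 0.34 | 0.539 | 0.583 | 15.4 months | 7.7 months |
| Consolidation | 0.20 | 0.805 | 0.447 | 10.3 months | 5.2 months |

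The rounded event rates in Section 9.2 give 0.631, 0.583 and 0.449. Section 9.4 itself gives historical medians of 1.5 years, 1.3 years and 10.4 months, which match the fifth column. The rows used for the 50% have half those medians, so they are not the historical null.

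**3. Read the tables at the historical one-year rates.**

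- Table 5: 0.632 lies beyond the last row (0.60, stop 0.06, average N 24.07). Not stopping is at least 0.94 and average N at least 24.1.
- Table 6, linear interpolation at 0.583: stop = 0.09 − 0.83 × (0.09 − 0.02) = 0.032, so not stopping is 0.968. Average N = 23.86 + 0.83 × (24.73 − 23.86) = 24.6.
- Table 7, linear interpolation at 0.447: stop = 0.06 − 0.47 × (0.06 − 0.01) = 0.036, so not stopping is 0.964. Average N = 24.2 + 0.47 × (24.87 − 24.2) = 24.5.

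By these tables the screen saves less than one of 25 patients on average (25 − 24.07 = 0.93 at most). The rows treated as null suggest 25 − 18.51 = 6.5, 25 − 19.2 = 5.8 and 25 − 18.17 = 6.8.

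**4. Recompute the rule.** This is an exact binomial recursion with the Section 9.4 rule, the plan's priors, the 70% cut-off, complete one-year outcomes and stopping looks at 10, 15 and 20. An arm stops at or below these event-free counts:

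- myeloablative: 3/10, 4/15, 6/20
- non-myeloablative: 2/10, 4/15, 5/20
- consolidation: 1/10, 2/15, 3/20

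The recursion matches all 15 tabled stopping probabilities within 0.03 and all 15 average N values within 0.38. At the historical one-year rates, not stopping is 0.965, 0.976 and 0.970, with average N 24.5, 24.7 and 24.6. Adding a look at 25 worsens the fit (largest difference 0.072) but leaves these probabilities at 0.964, 0.976 and 0.970.

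**5. Allow for staggered entry.** Poisson accrual at 10 per year, looks at enrolment of 10, 15, 20 and 25, four candidate effective-sample-size formulas, 2,500 runs each:

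| Arm | Stop at the row treated as null | Not stopping at the historical rate |
|---|---|---|
| Myeloablative | 0.41–0.53 | 0.89–0.98 |
| Non-myeloablative | 0.40–0.56 | 0.88–0.97 |
| Consolidation | 0.39–0.58 | 0.84–0.98 |

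**6. Place the alternatives.** S(t) = 0.5^(t/median). A median of 3.1 years gives one-year RFS 0.80 and two-year RFS 0.64. A median of 18 months gives 0.63 and 0.40. The last table rows are 0.60, 0.60 and 0.50, so none covers its alternative on the labelled axis. For the test as simulated, those rows' power values (0.69, 0.88 and 0.95) are only floors.

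**7. Test the other reading.** If the axis were really two-year RFS, only Table 7's 0.40 row would match its alternative; Tables 5 and 6 would need a row at 0.64. A staggered-entry simulation of a two-year rule gives average N at the null of 21.6–22.5, 21.3–22.9 and 20.9–23.1, against the tabled 18.5, 19.2 and 18.2. That reading does not reproduce the tables.

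**The case against.** The strongest objection is that the leniency is deliberate. Section 9.4 openly compares one-year RFS with a two-year null, explains why, and accepts a permissive rule because of low toxicity, high relapse risk and poor outcome after relapse. Those reasons stand, and correcting the 50% changes neither the looks, nor the sample size, nor the separate GVHD rule in Section 9.5. But declaring a rule lenient does not make a wrong figure for its leniency right.

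A second objection concerns precision, and it stands in part. The exact calculation assumes complete one-year outcomes, which the plan would not have at its looks, and its close fit leaves out a look at 25. Staggered-entry versions reach down to 0.84 not stopping. With Kaplan-Meier-type effective sample sizes, or with all enrolled patients counted, average N is about 23.0 to 23.9, a saving of one to two patients. These versions fit the last table rows poorly (stopping 0.09–0.14 against the tabled 0.06, 0.02 and 0.01). The 94–97% and the saving of under one patient are therefore readings from the plan's 1000-run tables, and the true values await a re-run.

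Third, a complete-data binomial calculation has no time scale, so it cannot show which axis was simulated. That is correct. The one-year reading rests on the column labels and the Section 9.4 rule. If the axis were two-year, the tables would not describe that rule, and Section 9.4 would still need correction.

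Fourth, highlighting is lost in the text as supplied, so the intended power row cannot be seen. No printed row matches the alternatives on the labelled axis, whichever one was highlighted.

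**Conclusion.** The concern holds. Section 9.4 attributes to the historical rates a stopping behaviour that belongs to arms with about half the historical median RFS. Against the stated 50%, the risk of not stopping an arm at the historical rates is at least 0.94, about 0.97 and about 0.96 from the plan's tables, and 0.84 to 0.98 across the staggered-entry variants. Power at the stated alternatives cannot be found on the labelled axis.

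The column for rejecting H0 has the same problem. At the historical one-year rates it reads at least 0.69 (Table 5), 0.58 + 0.83 × 0.30 = 0.83 (Table 6) and 0.74 + 0.47 × 0.21 = 0.84 (Table 7). Because the rejection criterion is not given, neither type I error against history nor corrected power can be derived from the document.

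The result assumes exponential RFS, which is the plan's own model, a one-year axis as labelled, and RFS counted from study entry. On the last point Section 9.1.1 says: "The start time of RFS will be the date of first remission marrow following induction treatment". The simulation text does not say which origin it used. If the historical hazard ran from that earlier date and patients entered still in remission, their one-year RFS would be higher and stopping rarer still.

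**What to change.** Re-run the simulations on one time scale and state the RFS origin and the effective-sample-size formula used. For each arm add a row at the historical hazard (one-year RFS about 0.63, 0.58 and 0.45 if counted from entry) and a row at the stated alternative (0.80, 0.80 and 0.63). Replace the 50% sentence with the re-run figure. State the criterion behind the H0-rejection column, and give type I error and power at 25 patients for the two-year primary endpoint as the re-run finds them. Say which time point the priors describe, and bring the wording of Section 9.3 into line with Section 9.4.

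The one-year screen may stay, provided its actual stopping probabilities are shown. The cost is a simulation re-run and a rewrite of Section 9.4. The reported futility performance will look less favourable, because an arm at the historical rate would rarely be stopped by this screen.
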